8.3. Time Period and Frequency for Event Assessment and Follow-Up

8.3.1. Adverse Event Reporting

All AEs will be collected from the time of signed informed consent until the final visit.

Any AEs assessed as related to study participation (eg, protocol-mandated procedures, invasive tests, or change in existing therapy) will be collected from the time a subject consented to participate in the study up to and including any follow-up contact.

All SAEs will be recorded in the eCRF and reported to the Sponsor within 24 hours via email or phone (refer to Medical Monitor/Sponsor Information page for contact information) (see Section 8.4).

8.3.2. Follow-Up of Adverse Events

After the initial AE/SAE report, the Investigator is required to proactively follow each subject at subsequent visits/contacts. All SAEs and nonserious AEs will be followed until resolution, until the condition stabilizes, until the event is otherwise explained, or until the subject is lost to follow-up.

The Investigator will assess the outcome of each AE using the following criteria:

- **Recovered/Resolved:** The event has improved or subject recuperated.
- **Recovered/Resolved with sequelae:** The subject has recuperated but retained pathological conditions resulting from the prior disease or injury.
- **Recovering/Resolving:** The event is improving.
- **Not recovered/Not resolved:** The event has not improved or subject recuperated.
- **Unknown:** The outcome of the event is not known, not observed, not recorded, or refused.
- **Fatal:** Termination of life as an outcome of the AE.

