### **12.9.1 Adverse Events**

AE terms will be coded using the MedDRA dictionary. A treatment-emergent AE (TEAE) is defined as an AE that starts after the first dose of study medication. For subjects not rolling over to Open-label study, all reported AEs will be included in the Double-Blind phase summaries. For subjects rolling over to the Open-label study, all AEs with an onset date on or before the Week 12 visit date will be included in the Double-Blind phase summaries.

If relationship to treatment is missing, the event will be conservatively treated as related to study drug. Missing severity will be imputed to the highest severity level (most severe).

All AEs will be listed by treatment and by subject, detailing the verbatim term given by the investigator, the preferred term (PT), system organ class (SOC), onset date and time, end date and time, duration (days), CTCAE grade, outcome, relationship to study drug/treatment, action taken with study drug/treatment, other action taken to treat the event, seriousness and criteria for seriousness. Serious AEs (SAEs), TEAEs leading to study discontinuation, TEAEs related to study drug will also be listed separately. The following adverse event of special interest (AESIs) will be identified and listed separately: contact dermatitis, folliculitis, and headache.

AEs will be summarized by treatment and overall as incidence rates of:

- Any AE
- Any TEAE
- Any AESIs
- Any treatment-related TEAE, including definitely, probably, and possibly related
- Any TEAE leading to study drug discontinuation
- Any SAE (non-Fatal)
- Any serious TEAE
- Death
- Treatment-related Serious TEAE
- Serious TEAE leading to study drug discontinuation

Individual PTs will be summarized by treatment according to the following:

- All TEAEs by SOC in alphabetical order and PT in descending order of combined frequency (also for treatment-related TEAEs, TEAEs leading to study discontinuation and serious TEAEs)
- All TEAEs by SOC, PT, and maximum CTCAE grade
- All TEAEs by SOC, PT, and maximum causality (not related, related) to the study drug

In addition, TEAEs and serious TEAEs will be summarized by SOC (alphabetical order) and PT (descending order) for the following subgroups:

- Age (<65 and >= 65 years old)
- Sex
- Race (White, Other)

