At each level of summarization, a subject will be counted once if he/she reported one or more events. The severity of TEAEs and relationship to study drug will be summarized in a similar manner. For summaries of relationship to study drug, a subject will be classified according to the closest relationship. For summaries of TEAE CTCAE grade, a subject will be classified according to the worst grade.

For AESIs, summarization will be more extensive, reflecting the more detailed information collected. Information summarized will include number of events per subject, earliest onset day, duration (in days), causality, grade and seriousness of AESIs, outcome, actions taken with study drug, assorted physical characteristics of the AESIs, and demographic/baseline characteristics and PGA status of the subjects experiencing them. Each type of AESI will be summarized separately. If a subject has more than one treatment-emergent occurrence of an AESI, the subject's maximum duration, highest levels of causality and seriousness, maximum grade and generally the most extreme level of each characteristic will be summarized. If an AESI was ongoing at EOS, it will not be included in the duration summary.

A Kaplan-Meier figure will be generated for each AESI of time to first event. Subjects not experiencing the AESI will be censored at the date of study completion or discontinuation.

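### Protocol 8.3.2 lets improvement alone meet the criterion for Recovered/Resolved, so an adverse event that is still present can be coded as resolved

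*Protocol*

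**What the plan says.** Protocol 8.3.2 presents its outcome list as the criteria by which the investigator assesses every AE. Leaving aside *Unknown* and *Fatal*, there are four clinical outcomes:

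- The code *Recovered/Resolved* applies when this holds: "The event has improved or subject recuperated".
- Recovery that leaves lasting damage has a separate code, *with sequelae*, whose test is worded as: "The subject has recuperated but retained pathological conditions resulting from the prior disease or injury".
- An event on its way to recovery is coded *Recovering/Resolving* if the following is true: "The event is improving".
- Lack of recovery is coded *Not recovered/Not resolved*, with this test: "The event has not improved or subject recuperated".

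The same section sets the end of follow-up: "All SAEs and nonserious AEs will be followed until resolution, until the condition stabilizes". Explanation of the event and loss to follow-up are the other end points. Protocol 8.4.1 repeats this rule for serious AEs, and 8.2.1.2.2 and 8.2.1.2.3 also separate resolution from stability for Grade 3 and Grade 4 events.

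The SAP uses the outcome code in two places, both in 12.9.1. The listing of all AEs includes "CTCAE grade, outcome, relationship to study drug/treatment, action taken with study drug/treatment". The summaries for each type of AESI (contact dermatitis, folliculitis and headache) include "causality, grade and seriousness of AESIs, outcome, actions taken with study drug". Where a subject has repeat occurrences of an AESI, "generally the most extreme level of each characteristic will be summarized".

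**The concern.** A code labelled resolved should mean that the event is over. As written, partial improvement is enough, and neither document states elsewhere that the event must have ended before the code is used. The definition of full recovery is also looser than that of recovery with sequelae, which requires recuperation. That ordering is hard to believe was intended.

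What is at stake is how the reversibility of AEs is described. A contact dermatitis that improved but persisted could appear as resolved in the listing and in the AESI outcome table. With roughly 50 to 60 sites, some staff may code by the label and others by the written criterion, so the same clinical state could receive different codes.

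**Working it through.** There is no figure in the plan to reproduce. The check applies each clinical definition to each state an AE can be in when its outcome is assessed. The subject is alive and the state is known, so *Unknown* and *Fatal* do not apply.

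One definition can be read in two ways. The *Not recovered/Not resolved* wording can mean neither improved nor recuperated (reading 1), or that at least one of the two is lacking (reading 2). Both are carried through. In states A to C the subject has not recuperated; in D and E the subject has.

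| State of the AE | Codes met, reading 1 | Codes met, reading 2 | After the fix |
|---|---|---|---|
| A. Present, has improved, still improving | Recovered; Recovering | Recovered; Recovering; Not recovered | Recovering |
| B. Present, improved, now stable | Recovered | Recovered; Not recovered | Recovering |
| C. Present, never improved | Not recovered | Not recovered | Not recovered |
| D. Gone, no sequelae | Recovered | Recovered | Recovered |
| E. Gone, with sequelae | Recovered; Recovered with sequelae | Recovered; Recovered with sequelae | Recovered with sequelae |

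State B step by step:

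1. *Recovered/Resolved* is met, because the event has improved.
2. *With sequelae* is not met, because the subject has not recuperated.
3. *Recovering/Resolving* is not met, because improvement has stopped.
4. *Not recovered/Not resolved* is not met on reading 1, because the event has improved. It is met on reading 2, because the subject has not recuperated.

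So on reading 1 the only clinical code available to a persisting event says that it is resolved. On reading 2 the same event is both resolved and not resolved. Either way the list fails for this state.

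State B is one the protocol expects. Its follow-up rule allows follow-up to stop at stabilization, as an end point distinct from resolution.

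The table shows where the definitions overlap or misfire. It does not measure effect: the states are not equally common, and the documents give no AE counts by outcome.

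**The case against.** The strongest reply is that each criterion is a label plus a gloss and should be read as a pair. *Recovered* against *Recovering*, and a completed tense against a continuing one, point a sensible investigator to the usual meaning. The follow-up rule supports this: if the section treats stabilization as different from resolution, a code labelled resolved should not take in a merely stable event. This stands in part. Many investigators will code correctly, and the double fit in state A largely disappears once label and tense are given weight. It does not rescue the definition, because the gloss is the stated criterion and it contradicts the label it is meant to explain.

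Stronger conclusions are tempting, and the documents do not support them:

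- A reader might infer that an improved, stable event can fit only the resolved code. That holds on reading 1 only.
- A reader might infer that AESI durations are shortened, or that study drug is restarted too early. SAP 12.9.1 leaves an AESI out of the duration summary if it is ongoing at end of study, without tying that status to the outcome code. Protocol 8.1.3 allows restart when the event resolves, but as part of investigator judgment and without reference to the code.
- A reader might infer that miscoding occurred, or that it favours one arm. The case report form and its completion guidance are not among the documents. The definitions are the same in both blinded arms, and SAP 12.9 plans no formal safety comparisons.

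There are also partial safeguards. The listing shows end date, duration and grade beside outcome. Protocol section 9 provides for querying inconsistent data, and SAP section 5 places data review before lock. Neither document states a specific check of outcome against end date. The per-subject rule for repeat AESIs means that one miscoded occurrence need not change a subject's row.

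**Conclusion.** The *Recovered/Resolved* definition is wrong as written, and the effect is minor. Followed literally, it allows an AE that is still present to be recorded as resolved. For an improved, stable event the code set either misclassifies it or contradicts itself. This rests on the plain wording of Protocol 8.3.2 and on the absence of any other definition of resolved in the protocol or SAP. It does not depend on which reading of *Not recovered/Not resolved* is chosen.

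The size cannot be computed. The reach is limited to the descriptive AE outcome listing and the AESI outcome summaries, where the resolved share could be overstated. AE outcome is not one of the trial's safety endpoints. Incidence, grade, seriousness, causality, the efficacy results and comparisons between arms are not shown to be affected.

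**What to change.** Reword the outcome definitions in Protocol 8.3.2:

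- *Recovered/Resolved*: the event is no longer present, or the subject has returned to the pre-event state, without sequelae.
- *Recovered/Resolved with sequelae*: the event has ended and residual pathology remains.
- *Recovering/Resolving*: the event has improved but is still present, whether or not improvement is continuing.
- *Not recovered/Not resolved*: the event is still present with no improvement.

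Each state in the table then has exactly one code. Placing an improved, stable event under *Recovering/Resolving* is a convention, since improvement has stopped. It could instead go under *Not recovered/Not resolved* if that code were defined as still present and not improving. What matters is that one code is named and that it is not the resolved one. Including the words on sequelae in the first definition also removes the overlap in state E.

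The cost is a wording change, with no new data and no change to the SAP tables. If data collection has ended, check outcome against end date in the data review before lock and query any event coded as resolved that has no end date.

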8.4. Reporting Procedures

8.4.1. Serious Adverse Event Reporting

When an Investigator determines that an AE meets the protocol definition of an SAE during the study, he/she must notify the Sponsor using an SAE Report Form **within 24 hours of the study site personnel's knowledge of the event**, regardless of the Investigator assessment of the relationship of the event to study drug. Relevant information will be entered on the AE page and on all other applicable pages of the eCRF; source documentation should not be sent with the SAE Report Form unless requested.

Follow-up information received on SAEs should be faxed to the Sponsor within 1 business day of receipt (refer to Medical Monitor/Sponsor Information page for contact information). This information should be included on a follow-up SAE form and placed with the original SAE information.

All SAEs will be followed until resolution, until the condition stabilizes, until the event is otherwise explained, or until the subject is lost to follow-up.

The completed SAE Report form should be submitted via email or fax to the SAE Reporting Contact which can be found on the [Medical Monitor/Sponsor Information Page](#) of this protocol.

Do not delay reporting a suspected SAE in order to obtain additional information. Any additional information, if collected, can be reported as a follow-up to the initial report.

8.4.2. Regulatory Reporting Requirements for Serious Adverse Events

Prompt notification by the Investigator to the Sponsor of SAEs (even for non-interventional post-marketing studies) is essential so that legal obligations and ethical responsibilities towards the safety of subjects and the safety of a product under clinical investigation are met.

The Sponsor has a legal responsibility to notify both the local regulatory authority and other regulatory agencies about the safety of a product under clinical investigation. The Sponsor will

comply with country-specific regulatory requirements relating to safety reporting to the regulatory authority, IRB/IEC, and Investigators.

Investigator safety reports are prepared for suspected unexpected serious adverse reactions according to local regulatory requirements and are forwarded to Investigators as necessary.

An Investigator who receives an Investigator safety report describing a SAE(s) or other specific safety information (eg, summary or listing of SAEs) from the Sponsor will file it with the Investigator's Brochure and will notify the IRB/IEC, if appropriate, according to local requirements.

8.5. Pregnancy Management and Reporting

Any female subject who becomes pregnant during the study will be withdrawn. Details will be collected for all pregnancies in female subjects and female partners of male subjects that begin after the start of dosing and through the Follow-up visit. Pregnancy is not automatically considered an AE.

If a pregnancy is reported, then the Investigator should complete a Pregnancy Report Form and submit via email or fax to the Pregnancy Reporting Contact for which contact information can be found on the [Medical Monitor/Sponsor Information Page](#) of this protocol, within 2 weeks of learning of the pregnancy. The subject will also be followed to determine the outcome of the pregnancy. Information on the status of the mother and child will be forwarded to the Sponsor. Generally, follow-up will be no longer than 6 to 8 weeks following the estimated delivery date. Any premature termination of the pregnancy will be reported.

Any SAE occurring in association with a pregnancy brought to the Investigator's attention after the subject has completed the study and considered by the Investigator as possibly related to the study drug must be promptly reported to the Sponsor or the Sponsor's representative.

The Investigator must attempt to collect pregnancy information on any female partners of male study subjects who become pregnant while the subject is enrolled in the study. Pregnancy information must be reported to the Sponsor or the Sponsor's representative as described above. The partner will also be followed to determine the outcome of the pregnancy. Information on the status of the mother and child will be forwarded to Sponsor or the Sponsor's representative. Generally, follow-up will be no longer than 6 to 8 weeks following the estimated delivery date. Any premature termination of the pregnancy will be reported on the pregnancy report form.

8.6. Safety Oversight

No independent Data Monitoring Committee will be used for this study; however, the Sponsor (including the Medical Monitor) will monitor safety on a periodic basis throughout the study.

9. DATA MANAGEMENT

For this study, subject data will be entered into the Sponsor-defined eCRFs, transmitted electronically to the Sponsor or designee, and combined with data provided from other sources in a validated data system.

Management of clinical data will be performed in accordance with applicable Sponsor standards and data cleaning procedures will be used to ensure the integrity of the data, eg, errors will be corrected, and inconsistencies queried in the data.

Adverse events and relevant medical history will be coded using the most current version of the Medical Dictionary for Regulatory Activities (MedDRA). Concomitant medications will be coded with the most current version of World Health Organization Drug Global Dictionary (WHODrug Global).

The Investigator will retain original source documents and the Sponsor will receive CRF-required data as electronic datasets. Subject initials will not be collected or transmitted to the Sponsor.

10. STATISTICAL CONSIDERATIONS AND DATA ANALYSES

This study will evaluate the efficacy and safety of tapinarof cream, 1% compared with vehicle control cream in adults with plaque psoriasis.

10.1. General Considerations

All study data will be summarized by treatment group using descriptive statistics. Categorical variables will be reported using frequency and percentage (eg, gender, race). Continuous variables will be reported using number of patients, mean, standard deviation (SD), median, minimum, and maximum. All efficacy and safety data will be listed by subject.

10.2. Determination of Sample Size

It is assumed that the proportion of subjects who achieve PGA score of clear (0) or almost clear (1) with a minimum 2-grade improvement from Baseline at Week 12 will be 40% for subjects receiving tapinarof compared with 15% for subjects receiving vehicle control. With 500 subjects randomized in a 2:1 ratio (approximately 333 subjects receiving tapinarof cream, 1% and approximately 167 subjects receiving vehicle cream) there will be > 99% power for a statistical significance (2-sided $p < 0.05$). If tapinarof response rate is 35%, and vehicle response rate is 20%, the power will be > 94%. The power is calculated from a Fisher Exact sample size calculation which is conservative. It is assumed that up to 25% of the subjects will be lost to follow-up by 12 weeks. These subjects will be included in the primary analysis using the multiple imputation method.

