Determination of Sample Size: It is assumed that the proportion of subjects who achieve PGA score of clear (0) or almost clear (1) with a minimum 2-grade improvement from Baseline at Week 12 will be 40% for subjects receiving tapinarof cream, 1% compared with 15% for subjects receiving vehicle control cream. With 500 subjects randomized in a 2:1 ratio (approximately 333 subjects receiving tapinarof cream, 1% and approximately 167 subjects receiving vehicle cream), there will be $> 99\%$ power for a statistical significance (2-sided $p < 0.05$). If the tapinarof response rate is 35%, and the vehicle response rate is 20%, the power will be $> 94\%$. The power is calculated from a Fisher Exact sample size calculation which is conservative. It is assumed that up to 25% of the subjects will be lost to follow-up by 12 weeks. These subjects will be included in the primary analysis using the multiple imputation method.

Efficacy Analyses: All efficacy analyses will be based on the Intent-to-Treat (ITT) population and will be repeated for the Per Protocol (PP) population only for the primary and secondary efficacy endpoints as supportive analysis. The primary efficacy endpoint will be analyzed using a Cochran–Mantel–Haenszel (CMH) test stratified by PGA score at Baseline (PGA scores of 2, 3, or 4). The same method used for the primary analyses will be used to analyze all dichotomized secondary endpoints. The secondary endpoints will be tested sequentially in order, and testing will stop if non-significance (2-sided $p \geq 0.05$) is observed. Other efficacy endpoints will be analyzed

using CMH test for proportions, and analysis of covariance (ANCOVA) model for continuous variables. CMH tests will be stratified by baseline PGA score, and ANCOVA models will include PGA score as a covariate. Open-label data will be summarized using summary statistics without testing.

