### 12.8.1 Primary Efficacy Analyses

The primary efficacy endpoint will be analyzed using a Cochran–Mantel–Haenszel (CMH) test stratified by PGA score at Baseline (PGA scores of 2, 3 or 4) based on the ITT population using the multiple imputation approach.

- For each multiple imputation dataset, the CMH option in PROC FREQ will calculate the adjusted estimate of the common relative risk of success (tapinarof/placebo) over all strata with its 95% confidence interval (CI).
- The logit-based version of the estimate and its confidence bounds will be log-transformed and the SE of the estimate of the log(relative risk) will be back-calculated from the log(confidence bounds) by assuming an asymptotic normal distribution.
- The estimates of the log(relative risk) and their standard errors for all the multiple imputation datasets will be input to PROC MIANALYZE to test the null hypothesis that tapinarof is not different from placebo. The p-value of the combined results will be reported for interpretation.
- PROC MIANALYZE will output an overall estimate of the log(relative risk) and its 95% CI. These will be exponentiated to produce an overall estimate of the relative risk and its 95% CI.

Sensitivity analyses in the ITT population will be conducted in which missing values are not imputed, i.e., Observed Cases (OC), or imputed as treatment failures (TF), and efficacy is tested with the CMH statistic as described above. Supporting analyses of the primary endpoint will also be performed

- in the PP population based on OC only,
- in the ITT population with missing values imputed by LOCF,

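### The 94% power at 35% vs 20% counts all 500 Week 12 outcomes as observed; at the plan's own 25% loss ceiling, Fisher power on observed cases is 85.3%

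*Protocol*

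**What the plan says.** Protocol Section 10.2, the Synopsis paragraph on sample size and SAP Section 7 carry the same calculation. About 333 subjects receive tapinarof and about 167 receive vehicle, tested two-sided at 0.05. In the main scenario response "will be 40% for subjects receiving tapinarof compared with 15% for subjects receiving vehicle control", with power above 99%. For the second scenario: "If tapinarof response rate is 35%, and vehicle response rate is 20%, the power will be > 94" per cent. The protocol adds: "The power is calculated from a Fisher Exact sample size calculation which is conservative".

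The next sentence reads: "It is assumed that up to 25% of the subjects will be lost to follow-up by 12 weeks". Those subjects are to enter the primary analysis by multiple imputation. No power is given for fewer than 500 observed outcomes, and the sample size is not inflated for the loss.

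The primary p-value does not come from Fisher's test. SAP Section 12.8.1 takes a relative risk stratified by baseline PGA from each imputed dataset and pools on the log scale: "The estimates of the log(relative risk) and their standard errors for all the multiple imputation datasets will be input to PROC MIANALYZE". An analysis of observed cases, using the stratified method, is planned as a sensitivity analysis.

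**The concern.** The paragraph puts a power figure, the word conservative and a 25% loss assumption side by side, and does not say that the first leaves out the last. A reader will naturally take 94% as the power the trial has after the expected loss, perhaps with a margin because Fisher's test was used.

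At stake is how the 35% vs 20% scenario is read. It is the plan's own cautious case, and the only one in which power is far enough from 100% to be informative. The reader is told that the risk of missing that effect is under 6%.

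**Working it through.** **Inputs** (Protocol 10.2): response 35% vs 20%; 333 and 167 subjects; two-sided alpha 0.05; Fisher exact test; loss of up to 25%. Loss by arm is not given. I assume that it is equal in both arms and unrelated to outcome, so 25% loss leaves about 333 × 0.75 ≈ 250 and 167 × 0.75 ≈ 125 observed.

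**Method.** Enumerate every pair of responder counts (x₁, x₂). The probability of each pair is Bin(x₁; n₁, p₁) × Bin(x₂; n₂, p₂). The two-sided Fisher p-value is the sum of the hypergeometric probabilities no larger than the observed one. Power is the total probability of the pairs with p < 0.05.

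**Step 1: reproduce the stated figure.** At 333/167 and 35% vs 20%, power is 93.8%. At 334/166 it is 93.8%, and at 332/168 it is 93.9%. It first passes 94% at 334/167 (94.05%), which is 501 subjects. So the stated figure is reproduced to rounding, and only with no loss. At 40% vs 15%, 333/167 gives more than 99.9%, which agrees with the plan.

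**Step 2: apply the loss assumption (35% vs 20%).**

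| Loss | Observed (tapinarof/vehicle) | Fisher power | Chance of missing the effect |
|---|---|---|---|
| 0% | 333/167 | 93.8% | 6.2% |
| 5% | 316/159 | 93.0% | 7.0% |
| 10% | 300/150 | 91.5% | 8.5% |
| 15% | 283/142 | 89.8% | 10.2% |
| 20% | 266/134 | 87.8% | 12.2% |
| 25% | 250/125 | 85.3% | 14.7% |

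At 25% loss, rounding the arms differently gives 84.9% (249/125) to 86.0% (250/126). With 375 observed but unequal loss, power is 82.5% at 266/109 and 87.6% at 233/142. The main scenario at 250/125 gives 99.9%.

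**Step 3: hand check with the pooled z test.** Power = Φ[(0.15 − 1.96·se₀)/se₁], where se₀ uses the pooled rate and se₁ the separate rates.
- 333/167: se₀ = 0.0434, se₁ = 0.0405, so Φ(1.60) = 94.5%.
- 250/125: se₀ = 0.0502, se₁ = 0.0468, so Φ(1.10) = 86.5%.

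The drop is again about 8 points, so it does not depend on the choice of Fisher's test.

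**Step 4: the statistic actually planned.** The primary p-value rests on the log relative risk. A simple unstratified approximation is Φ[ln(0.35/0.20)/se − 1.96], with se² = 0.65/(0.35·n₁) + 0.80/(0.20·n₂).
- 333/167: se = 0.172, so Φ(1.30) = 90.3%.
- 250/125: se = 0.199, so Φ(0.86) = 80.5%.

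A simulation of the stratified statistics (400,000 trials per setting, no imputation) assumed baseline PGA strata of 10/80/10%, the same response rates in each stratum, and loss equal by arm and unrelated to outcome. It gave:

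| Stratified statistic | Complete data | Observed cases, 25% loss |
|---|---|---|
| CMH test | 94.5% | 86.5% |
| Log relative risk | 91.5% | 79.9% |

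With response rates that differ by stratum but average 35% and 20%, the log relative risk gave 92.6% and 82.6%. None of these is the power of the multiple-imputation analysis. They show that loss costs each statistic power, and that Fisher is not conservative relative to the log relative risk even with complete data.

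**The case against.** Four points can be made for the plan.

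- **The figure is not an arithmetic error.** The arm sizes are approximate, exact Fisher power moves in small jumps with N, and 334/167 gives 94.05%. This stands: the 0.2-point gap is rounding, and the substance is the missing allowance for loss.
- **The lost subjects are imputed, not dropped, so 85.3% is not the power of the planned analysis.** This also stands as a limit on the claim. The imputation model (SAP Section 9) uses earlier PGA scores and may recover information. A rough simulation used assumptions outside the documents: a continuous severity score, visit correlations of 0.5 to 0.85, 25% loss at random, Week 4 or Week 8 observed, an unstratified log relative risk and 1,500 trials per setting. It put imputation at about 89–92%, against 85–86% for observed cases and 93–95% with complete data. Recovery was partial even there. A five-point PGA, earlier dropout or the stratified statistic could recover less.
- **The stratified CMH test is named elsewhere,** including in the Synopsis paragraph straight after the calculation. That is so, but nothing ties the power figure to that test or says that it needs complete outcomes.
- **25% is a ceiling and the consequence is small.** Both are fair. The full range is shown above for that reason, and no sample size or decision rule is in question.

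**Conclusion.** The point holds. The stated 94% is Fisher power with all 500 Week 12 outcomes observed (exact value 93.8%). Under the loss assumed in the same paragraph, Fisher power on observed cases falls to 91.5% at 10% and 85.3% at 25%, a drop of 8.4 points at the ceiling. This rests on loss that is equal by arm and unrelated to outcome.

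Multiple imputation would probably recover some of the drop. How much cannot be worked out from the documents, which give neither visit-to-visit correlation nor dropout timing. Pooling adds between-imputation variance, so full recovery should not be presumed. Calling the calculation conservative describes the choice of test and not the treatment of missing outcomes.

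The main scenario is unaffected and N = 500 is adequate. This is a stated power that should be corrected, not a flaw in the design.

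**What to change.** Keep N = 500 and the analysis as planned. In the Synopsis, Protocol Section 10.2 and SAP Section 7, replace the second-scenario sentence with wording such as:

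> *With Week 12 outcomes for all 500 subjects, Fisher power at 35% vs 20% is about 94%. With 10% or 25% of outcomes missing, equally by arm and unrelated to response, Fisher power on observed cases is about 91.5% or 85%. At 40% vs 15% it remains above 99%. These Fisher figures are not the power of the planned multiple-imputation analysis, which pools stratified log relative risks.*

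If the sponsor wants a figure for the planned analysis, simulate it on the pooled log relative risk. State the assumed stratum rates, visit correlation and dropout pattern, and report complete-data power of the same statistic beside it.

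The cost is wording in three places and one less favourable stated figure, with no extra patients and no change to the analysis.
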